Protocol Number:

Video-Assisted Speech Technology-003

Protocol Date and Version #:

2/28/23 - version #3

Study Title

Video Assisted Speech Technology to enhance functional language abilities in individuals with Autism Spectrum Disorder

Investigators (including sub-investigators)

[name], M.A. CCC-SLP/CAS

[name], M.S. CCC-SLP/CAS

Address / Phone - Contact details

[name]

[name]

Source of external funding

National Institutes of Health (NIH)

Hypothesis

Users of the VR integrated VAST application will show improved functional language abilities and oral motor coordination skills.

Background

Autism Spectrum Disorder (ASD) is a neurodevelopmental communication disorder resulting in functional language and behavioral delays affecting over 3.5 million Americans. These delays vary with the severity of symptoms that present in ASD. Individuals may be verbal and possess stronger functional language abilities whereas 25% of people in the ASD population are minimally verbal or non-verbal, having increased communication challenges. ASD limits many aspects of speech such as vocabulary acquisition where the individual retains a limited lexicon. This restriction on word choice leads to further limitations in the development of sentence structure. Conversation is kept to simple requests and commands and only basic topics are maintained for discussion, preventing the expression of abstract ideas. Alongside linguistic acquisition, oral-motor coordination is a crucial part of speech production. Students with ASD struggle with acquiring the necessary motor skills needed for speech articulation and activities such as chewing.

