Three main metrics will be measured during the pilot study: *Percentage of Correctly Transcribed Words Using ASR, Articulation Accuracy, and Mean Length of Utterance (MLU)*. These metrics will show whether there has been improvement in the participant’s functional language abilities, and oral motor coordination skills. They will be

analyzed by several trained staff members who will observe each recorded and monitored session.

Subject Selection

Recruiting: Subjects will be recruited by contacting (e.g. email or telephone) teachers and professionals (e.g. speech-language pathologists and behaviorists) who work with children with autism, aged 4 to 8. The research team will reach out to school administrators, teachers, and specialists through the iTherapy network of contacts to recruit eligible K-2 students diagnosed with ASD and their teacher or specialist. The VR-based VAST platform is designed for use with early elementary school-aged students (grades K-2). In order to conduct the intervention and gather data that would be useful for further development of the product, the research study must include early elementary school students.

In order to recruit enough children within the study's target population and to encourage retention, the study team will use online advertising via social media and other platforms (e.g. Craigslist) to reach participants. All participants will be given an Apple device (iPhone 6 for VR or refurbished iPad mini for 2D) for participating in the study and a free download of InnerVoice (valued at \$99.99), an iOS AI-powered communication app that uses video self-modeling, designed and sold by iTherapy.

Number of participants: 6

Inclusion/Exclusion criteria: All participants will be recruited via campaigns posted on social media and/or other platforms: parents/guardians will be provided consent forms and all information regarding inclusion/exclusion criteria.

Children **under the age of 18** will be recruited and all protections mandated by NIH policy afforded to them.

In order to protect participants and their families from COVID-19 exposure, participants will undergo Aim 3's procedures within their homes: the subjects' data will be collected using a HIPAA-compliant telehealth video-streaming platform. The goal of this

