Primary	Change in Percentage of Correctly Transcribed Words Using Automatic Speech Recognition	Seven weeks--each subject participated in the study twice a week over a 7-week period for a total of 14 sessions. The first and last sessions (session #1 and session #14) were reserved for pre-test and post-test language sample collection and assessment.	15-minute pre- and post-testing was performed using speech recognition software and transcribed by a licensed speech pathologist. Differences pre- and post-intervention were compared across groups and within groups.
Primary	Change in Articulation Accuracy	Seven weeks--each subject participated in the study twice a week over a 7-week period for a total of 14 sessions. The first and last sessions	Change in % of correct phonemes in each attempted stimulus

		(session #1 and session #14) were reserved for pre-test and post-test language sample collection and assessment.	
Primary	Change in Mean Length of Utterance (MLU)	Seven weeks--each subject participated in the study twice a week over a 7-week period for a total of 14 sessions. The first and last sessions (session #1 and session #14) were reserved for pre-test and post-test language sample collection and assessment.	Participants (aged 4 to 8 years) were given a pre- and post-test 15-minute language sample. MLU was calculated for tests and gain from pre-test to post-test was compared.
Secondary	Parent Perceptions of Communication Changes Resulting from Study Participation	Seven weeks--each subject participated in the study twice a week over a 7-week period for a total of 14 sessions. The first and last sessions (session #1 and session #14) were reserved for pre-test and post-test language sample collection and assessment	Parent observations -- perceptions of changes in their children's motor-speech, behavioral, and social communication skills after having participated in the study

Secondary	Change in Type-Token Ratios	Seven weeks--each subject participated in the study twice a week over a 7-week period for a total of 14 sessions. The first and last sessions (session #1 and session #14) were reserved for pre-test and post-test language sample collection and assessment.	A type-token ratio measures the total number of unique words in a given segment of language.

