Secondary	Change in Response Rate to Treatment Stimuli	Seven weeks--each subject participated in the study twice a week over a 7-week period for a total of 14 sessions. The first and last sessions (session #1 and session #14) were reserved for pre-test and post-test language sample collection and assessment.	Response rate gain measured whether there were any significant changes in how often children responded to pre- and post-testing stimuli after having received treatment between the iPad Pro and VR goggles groups.

Risk / Safety Information

Participants in this study will face little to no harm, risks, or discomfort. Participants will undergo the Impact Metrics within their own homes via a HIPAA-compliant telehealth video stream in order to minimize the risk of COVID-19 exposure. Additionally, all equipment affiliated with the study will be cleaned and disinfected, following CDC guidelines, prior to the subjects receiving the equipment.

Participants will face no greater than minimal risk during the implementation of Aim 3's Impact Metrics. Each assessment session will last 30 minutes (+/- 5 minutes) twice per week. During the course of each assessment session, the participants will interact with known adults to decrease the chances of them feeling uncomfortable. As the software is

100% virtual, no adverse effects, risks, or discomforts are anticipated, other than what the participant may experience looking at a typical tablet screen or wearing VR goggles. Additionally, the hardware used in this study is designed to be worn for long periods of time with minimal to no discomfort.

However, the research team recognizes that it is possible that some participants may experience feelings of frustration, embarrassment, or fatigue through participation due to the amount of sensory integration within the particular treatment. It is recognized that the issue of sensory and stimulus overload is common in children with ASD. Children on the spectrum sometimes experience inability to focus or distress when exposed to a surplus of stimuli. Avoiding this overload is not a matter of simplifying learning materials but rather managing the perceptual load children are exposed to.

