sensory and stimulus overload is common in children with ASD. Children on the spectrum sometimes experience inability to focus or distress when exposed to a surplus of stimuli. Avoiding this overload is not a matter of simplifying learning materials but rather managing the perceptual load children are exposed to.

Should any Adverse Events (AEs), Serious Adverse Events (SAEs) — injuries, seizures, or emotional distress — and Unanticipated Problems Involving Risks to Subjects or Others occur, a session will be ceased immediately and a report submitted to the IRB within 48 hours by the on-site researcher. If an SAE were to occur — such as an injury or seizure — staff will contact emergency medical services to ensure the subject's safety. Staff will receive training in communication and behavioral de-escalation strategies, whose aim is to reduce subjects' exposure to emotional distress. The PI and Co-investigator, both certified autism specialists, will be responsible for implementing the training.

All stimuli and engagement topics will be thoroughly vetted to reduce any discomfort on the part of the participant. Research staff will be advised to immediately cease engagement upon any visual sign of participant discomfort. Participants will only participate in the study as a supplement, and not a replacement, of prescribed or existing therapies.

Monitoring and reporting of Adverse Events/Serious Adverse Events

The research team will monitor subjects' exposure to adverse events/SAE throughout the study. For example, we will ensure that the methods of data collection do not invade the privacy of students, parents, teachers, or schools. We will monitor participation and responses to oversee and reduce potential feelings of frustration or embarrassment. Additionally, all children using the VR headsets will be required to sit so as to avoid

falling or suffering other injuries that might occur from standing or walking while wearing the headsets.

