While all efforts will be made to keep data confidential, there is a small chance that participation in research may cause a loss of privacy. There is also a small risk of data loss and misuse or breach of private information. No physical, social, cultural, financial, legal, or other risks to subjects are expected from this study.

The data will be kept for ten years beyond the life of the project before all the files are destroyed, to allow for future longitudinal studies. While the data are kept for these additional years, the same storage protocols described above will be followed.

For the different group, electronic images (e.g., pdf), spreadsheets, and database files

Statistical Design and Power

We have used the following formula to calculate power and size of an experiments where there are >2 means:

$$n = 2 \left(\sigma \frac{z_{1-\alpha/(2\tau)} + z_{1-\beta}}{\mu_A - \mu_B} \right)^2$$

$$1 - \beta = \Phi \left(z - z_{1-\alpha/(2\tau)} \right) + \Phi \left(-z - z_{1-\alpha/(2\tau)} \right) \quad , \quad z = \frac{\mu_A - \mu_B}{\sigma \sqrt{\frac{2}{n}}}$$

Assumptions:

Power, $1-\beta$: 0.08

Type I error rate, α : 0.05

$\mu_A = 1$

$\mu_B = 2$

$\sigma = 1$

$\tau = 1$

Source: Chow S, Shao J, Wang H. 2008. Sample Size Calculations in Clinical Research. 2nd Ed. Chapman & Hall/CRC Biostatistics Series. page 71.

MLU, SIS, and articulation rate between groups will be tested using an ANOVA with pairwise comparisons.

may be created from paper-based field notes as researchers code data into an electronic form and de-identify (anonymize) response records. Data will then be protected as mentioned above.

IRB Review / Ethics / Informed Consent

As participants are children, all additional protections for children involved as subjects in research will be observed. We do not expect the study to involve greater than minimal risk and will obtain IRB approval of adequate provisions for soliciting the assent of the children and the permission of their parents or guardians.

The study involves children with ASD. Informed written consent from parents/guardians of the child participants is required prior to beginning any part of the study. Parents/guardians will be present at all times during the testing and will be able to stop

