We will use the data to examine whether the VAST VR system helps children with autism between the ages of 5 to 8 years improve their speech intelligibility, impact their articulation rate, and expand their MLUs. Further, the data obtained in this study will guide future design improvements for the VAST system. The overall intended use for the VAST system will be in special education classrooms for children who struggle with functional language acquisition and motor abilities. Students will be able to improve upon their oral coordination during their in-school therapy sessions which may last between one to three hours. The skills they learn will then be applied to their classwork and their daily interactions with peers and teachers. As their language abilities improve, teachers and students will be able to improve their cooperation and social interaction. By using the VAST system, students will be better able to understand and process the speech of their teachers and become more integrated in the classroom setting. Each student who participates in special education will require the use of a tablet or smartphone, VR goggles, and BC headphones.

The knowledge gained by this study has the potential to provide students with ASD with a comprehensive language education. The risks noted in the above section are minimal and reasonable in light of the benefits of the proposed study. Participation in this study will benefit all participants by supplementing their existing in-school therapy sessions while providing minimal to no risk.

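### The hypothesis names no comparator and is not tied to the between-group test, so a pre/post gain within the VR arm would satisfy it even if 2D children gained as much

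*Combined protocol and SAP*

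**What the plan says.** - **Hypothesis:** "Users of the VR integrated VAST application will show improved functional language abilities and oral motor coordination skills". The 2D tablet arm is not mentioned.
- **Study Goals and Objectives, Aim 3:** "These metrics will show whether there has been improvement in the" participant's abilities. This is also worded as change from baseline.
- **Intended Use of Data:** "We will use the data to examine whether the VAST VR system helps children with autism". Again there is no comparator.
- **Outcome Measures, speech-recognition (ASR) row, primary:** "Differences pre- and post-intervention were compared across groups and within groups".
- **Outcome Measures, MLU row, primary:** "MLU was calculated for tests and gain from pre-test to post-test was compared", without saying with what. The articulation row, also primary, gives only a change in percentage.
- **Outcome Measures, response-rate row, secondary:** worded as a comparison "after having received treatment between the iPad Pro and VR goggles groups".
- **Statistical Design and Power:** "MLU, SIS, and articulation rate between groups will be tested using an ANOVA with pairwise comparisons". This is the only named inferential test.
- **Risk / Safety Information:** "Participants will only participate in the study as a supplement, and not a replacement, of prescribed or existing therapies".

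Both groups use VAST, one in VR and one on a tablet. No untreated or usual-therapy-only group is planned. Testing takes place at session 1 and session 14, over seven weeks. No allocation method is described.

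**The concern.** As worded, the hypothesis is met if VR users improve from pre-test to post-test. The plan looks at that change for at least one primary outcome and does not say that the between-group result overrides it.

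Change within the VR arm cannot be credited to VR. The children keep their other therapies, they are tested twice, they are seven weeks older at the second test, and they practise VAST material that the 2D children also receive. All of these could produce a gain with no contribution from the headset. If both arms gained equally, a report could follow the stated hypothesis to the letter and still attribute the gain to VR. The 2D arm is the only element of the design that could separate VR from these shared influences, and the hypothesis does not use it.

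**Working it through.** **Plan's own figure.** There is none to reproduce. The plan gives no probability or success rule for within-arm change, and the power inputs in Statistical Design and Power concern a difference between two means. The calculation below is therefore an illustration.

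**Inputs from the documents**
- Type I error rate 0.05, two-sided by the printed formula with τ = 1.
- Arm size: Subject Selection gives 6 participants in total, and Study procedures gives 10 as two groups of five. Both are carried. The 6 are assumed to split 3 and 3.

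**Assumed inputs**
- One outcome, with normally distributed change scores.
- A paired t test within the VR arm.
- No VR effect: both arms share the same mean gain, d, in SDs of the change score. The documents give no value for d, so a range starting at zero is shown.

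**Within-arm test.** With n children, the paired t statistic has n − 1 degrees of freedom and noncentrality d√n. The chance of a favourable significant result is

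P = Pr{ t(n − 1, d√n) > t(0.975, n − 1) }.

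The critical values are 4.303 for n = 3 (2 df) and 2.776 for n = 5 (4 df). Example: at d = 1 and n = 5 the noncentrality is 1 × √5 = 2.236, which gives P = 0.401.

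| Shared gain d (SD of change) | 3 per arm: d√n | 3 per arm: P | 5 per arm: d√n | 5 per arm: P |
|---|---|---|---|---|
| 0 | 0 | 2.5% | 0 | 2.5% |
| 0.2 | 0.346 | 4% | 0.447 | 5% |
| 0.5 | 0.866 | 8% | 1.118 | 14% |
| 1 | 1.732 | 18% | 2.236 | 40% |

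**Between-arm test on change.** A shared gain cancels: (δ + d) − d = δ, where δ is the VR effect. With δ = 0, a two-sided 0.05 test favours VR in 2.5% of trials whatever d is. A simulation of 400,000 trials at each of d = 0, 0.5, 1 and 2, for 3 and for 5 per arm, gave 2.45% to 2.53%. This requires the arms to be comparable apart from the device.

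**Precision of the between-arm contrast.** The half-width of the 95% CI, in SDs of change and with the sample SD at its nominal value, is t(0.975, 2n − 2) × √(2/n).
- 3 per arm: 2.776 × √(2/3) = 2.27 SD.
- 5 per arm: 2.306 × √(2/5) = 1.46 SD.

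**The case against.** The strongest reply is that the plan is comparative. It has a 2D arm, its only named test is between groups, its power formula contrasts two means, and the response-rate outcome is worded between groups. It names no within-group test, p-value or significance rule, so the within-group comparison may be meant as descriptive. It is explicit for one primary outcome only. Aim 3 is a feasibility aim, and the data are also meant to guide design improvements.

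Most of this stands. It rules out the reading that the plan intends to declare VR effective from within-arm significance: no such rule is written, and the paired t test above is an assumption. It also argues against quoting an any-of-three-primaries error rate. Within-group wording is not explicit for the other two primaries, and part of such a rate would be multiplicity, which is present even with no shared gain.

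It does not close the gap. The ANOVA sentence is not linked to the hypothesis and does not make within-group change descriptive. Its outcome labels are also loose. SIS is undefined; it may be the intelligibility measure, in which case the ASR outcome is covered, but the text does not say so.

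Two further inferences go too far. One is that VR versus 2D is a contrast protected by the design: no randomisation or other allocation method is described, so comparability of the arms is not assured. The other is that a substantial natural gain over seven weeks is to be expected: the documents give no figure, and it may be small.

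**Conclusion.** The point holds as a gap between hypothesis and analysis. The stated hypothesis and intended use can be met by change within the VR arm, and nothing makes the existing between-group test govern the claim. That conclusion rests on the text alone and is firm.

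The size is conditional. It depends on an assumed shared gain and an assumed within-arm test. For a single outcome with no VR effect, the chance of a favourable significant VR change runs from the nominal 2.5% at no shared gain to 18% (3 per arm) or 40% (5 per arm) at 1 SD of change. At 0.2 SD the excess over 2.5% is small. The figures show the direction of the problem and how it grows; they do not predict this trial's error rate. The between-arm figure of 2.5% also rests on comparable arms, which the documents do not establish.

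**What to change.** 1. Restate the hypothesis and the intended use as the VR-minus-2D difference in pre-to-post change.
2. Make that difference, with its 95% CI, the only basis for any conclusion about a VR effect. State this in the outcome table and in Statistical Design and Power, using the same outcome names in both places.
3. Report within-arm change descriptively, without p-values, and note that it includes concurrent therapy, retesting, maturation and VAST content shared by the arms.
4. State how children were allocated, and present the contrast as a pilot estimate, since the arms have 3 to 5 children.

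The cost is wording and a statement of the allocation method; no new data are needed. The conclusion becomes narrower, because it concerns VR relative to 2D and not whether VAST VR helps in general. The interval will be wide, as the half-widths above show. If allocation turns out not to have been random, the contrast also needs a caveat on comparability, which rewording cannot remove.

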There are no events that would preclude a participant from continuing the intervention beyond withdrawal of assent or consent. As detailed in the Protections Against Risk above, the study presented no greater than minimal risk to participants. Trials will be stopped upon any visual observance of discomfort of the participant by the educator or trained professional (as detailed in the Protections Against Risk above). Data will be reported from all sites upon session completion – compliance and monitoring will be ensured by an on-site researcher who will collect session data. Further data security measures are detailed above in Collaborating Sites.

Any IRB and/or ISM/DSMB actions will be reported to the NIH within 72 hours of occurrence by the project PI [name].

Study Oversight

Data and safety will be monitored per NIH guidelines by project PI and IRB. Individual responsible for monitoring are:

1. [name] (project PI). [name] will ensure data security on a bi-weekly basis. Her position as CEO of iTherapy will include the monitoring of all data acquired from this study. She will ensure that all staff are adequately trained in the study protocol.
2. [name] (Co-Investigator). [name] will ensure safety on-site on a weekly basis. As the Chief Operations Officer at iTherapy, he is qualified to ensure data and safety during data collection.
3. IRB will ensure protocol adherence to acceptable safety practices.

Data Management

[Who will be collecting, analyzing the data? Do you plan to have an independent data analysis? Data retention (i.e. how long so you plan to maintain records for this study). Include statistical analysis plan (if applicable)]

Data formats — data will be stored in commonly-used file formats (e.g., .csv for survey data, .mp3 for audio files, .mov for screen recordings). There are no applicable metadata standards that will be applied to these data.

Dissemination — all data generated in this SBIR Phase I project is considered proprietary. A project report will be made available partial and/or aggregated form, upon request, to the intervention developers. A subset of the project report will be made available, upon request, to partner school districts or other organizations who assisted in recruiting participants.

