the activities at any time for any reason. Children will be asked for verbal consent. Participants will be informed that they can stop the sessions at any time for any reason. Because of the varying stimulatory thresholds of those with ASD, participants will be closely monitored by their teachers or health professionals for any visual or verbal sign of discomfort. Should any sign be observed, the participant's session will immediately be ceased.

Confidentiality

The confidentiality of all participants will be maintained throughout the life of the project, and the research team will institute and monitor robust data security protocols. All members of the research team will complete an online course covering research with human subjects and data security prior to the study's commencement. Data will be collected and stored on a secure online server. A code key will be created to assign a unique number to each study participant (i.e. P001). The data collected in this study will in no way be affiliated with the participants' medical record number or personnel files. All participant data will be stored on a secure, encrypted data storage device and/or a password protected and encrypted internet- or cloud-based storage system, which meets HIPAA privacy standards. The files will also be password encrypted. No data will be accessible from any source that is not password encrypted. The password will only be known to IRB-approved research study members.

Intended Use of Data

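### Adverse events are to be monitored throughout the study, but only in-session observation is described, with no symptom question after or between sessions

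*Combined protocol and SAP*

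**What the plan says.** The section Monitoring and reporting of Adverse Events/Serious Adverse Events undertakes to monitor children's "exposure to adverse events/SAE throughout the study".

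The detection methods described are these:

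- Risk / Safety Information: "Research staff will be advised to immediately cease engagement upon any visual sign of participant discomfort".
- Monitoring and reporting of AEs/SAEs: "Trials will be stopped upon any visual observance of discomfort of the participant", the observer being an educator or trained professional. The team will also follow participation and responses to limit frustration or embarrassment.
- IRB Review / Ethics / Informed Consent: teachers or health professionals watch the child "for any visual or verbal sign of discomfort".

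Other safeguards surround these. On session data: "Data will be reported from all sites upon session completion". Under Study Oversight, the co-investigator "will ensure safety on-site on a weekly basis". On parents: "Parents/guardians will be present at all times during the testing and will be able to stop". Children are also told that they may stop. VR users must sit, and a history of seizure disorder is an exclusion.

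When an AE, SAE or unanticipated problem occurs, the session stops and the IRB receives a report within 48 hours. On later use, however, the monitoring section states: "There are no events that would preclude a participant from continuing the intervention beyond withdrawal of assent or consent".

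Risk / Safety Information foresees fatigue, frustration, embarrassment, sensory overload, and whatever a child may feel from a tablet screen or goggles. Background puts the share of people with ASD who have little or no speech at 25%.

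**The concern.** The promise covers seven weeks, while each concrete method operates when someone is watching the child in a session. Some of the effects that the plan itself foresees, such as tiredness or overload, may show late or without an obvious sign. A child of 4 to 8 with limited speech may not volunteer them. The share of such children in this sample is not stated.

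Two things are at stake. First, delayed or subtle discomfort may go unnoticed before the child uses the device again, and no rule is described for pausing that use even after a recognised event. Second, if the trial later reports that no discomfort was seen, that would be weak support for tolerability, because nobody is described as having asked. No planned language outcome is touched, and no direction of bias is suggested.

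**Working it through.** There is no planned figure to reproduce, because the plan quantifies nothing on this point. The check is a reading of each relevant provision, followed by a count of exposures.

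**1. Does any provision describe a symptom question?**

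| Provision | Section | When it operates | Symptom question described? |
|---|---|---|---|
| Staff stop on visible discomfort | Risk / Safety Information | In session | No |
| Educator or professional stops on visible discomfort | Monitoring and reporting of AEs/SAEs | In session | No |
| Following participation and responses | Monitoring and reporting of AEs/SAEs | Not stated | No; no instrument or timing |
| Watching for visual or verbal signs | IRB Review / Ethics / Informed Consent | In session | No; relies on a sign or a volunteered complaint |
| Session data on completion | Monitoring and reporting of AEs/SAEs | End of session | No; content not given |
| Weekly safety role | Study Oversight | Weekly | No; method not given |
| Parent present and able to stop | IRB Review / Ethics / Informed Consent | During testing | No; no later reporting duty stated |
| Parent perceptions | Study procedures; Outcome Measures | After participation | No; covers motor-speech, behavioural and social communication change |
| Video review | Study procedures | After session | No; stated use is the outcome metrics |

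The named observers (an on-site researcher, educators, teachers) also sit awkwardly with sessions held at home by telehealth.

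**2. How often does a device go back into use with no described question beforehand?**

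Inputs: 14 sessions, two a week for seven weeks, with sessions 1 and 14 reserved for pre- and post-test (Outcome Measures). I assume that no device treatment takes place in those two.

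- Treatment sessions: 2 to 13, so 12 per child.
- Intervals ending in re-use: 2→3 through 12→13, so 12 − 1 = 11 per child.
- Mean interval: 7 / 2 = 3.5 days.

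Headset and tablet use should be counted apart, since the 2D arm has no headset.

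- Ten children, five on VR (Study procedures): 5 × 11 = 55 headset re-uses, and 55 tablet re-uses.
- Six children (Subject Selection), assuming a 3/3 split: 3 × 11 = 33 headset re-uses, and 33 tablet re-uses. Aim 3 names six children but two groups of five, so the split for six is not given.

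If the weekly safety role did include a symptom question, it would precede only about one re-use in two.

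**3. Context: share of the study period under observation.**

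- 14 × 30 min = 7.0 h (5.8 to 8.2 h at 25 to 35 min).
- Seven weeks: 7 × 7 × 24 = 1,176 h.
- 7.0 / 1,176 = 0.6% (0.5% to 0.7%).

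This shows how far the promised period exceeds the described method. It does not measure missed harm.

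**4. What follows a recognised event?** The 48-hour rule gives an IRB report. The monitoring section allows no event, other than withdrawal of assent or consent, to rule out continuing. Read together, review exists at IRB level, but no step between the event and that child's next session is described.

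**The case against.** The strongest reply is that this is a small study described as minimal risk, with a parent present and able to stop, VR users seated and seizure history excluded. The monitoring paragraph introduces its measures as examples, so the list need not be complete. Session forms and consent pages are not in the available text and could hold a symptom question or instructions to parents. The monitoring section also refers to headings (Protections Against Risk, Collaborating Sites) that do not appear there. No safety or tolerability outcome is planned, so no planned result depends on how symptoms are gathered.

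Most of this stands, and it limits the grade. It does not remove the point: the text does state a method, and that method is watching for signs, which is a weak way to find effects that the plan itself expects.

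Three stronger readings are tempting and are not supported:

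- A reader might infer from the sentence on continuing that nothing follows even when discomfort is reported. The 48-hour IRB report contradicts that for anything treated as an AE, and emotional distress is among the listed examples. The sentence concerns continuation and does not cancel the report.
- A reader might multiply the re-uses by some rate to estimate episodes of missed discomfort. The documents give no such rate, and nothing in them supports an assumed range.
- A reader might count every child's re-uses as headset exposures. That would pool tablet with headset use.

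**Conclusion.** The concern holds as a gap in the described method. Monitoring is promised for the whole study, but only in-session signs, volunteered complaints and general attention to participation and responses are described, and no rule covers a child's next device use after an event. Its size is 11 re-use intervals per child, or 55 headset re-uses (five VR users) or 33 (three VR users, assumed split). How many would follow missed discomfort is unknown.

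This rests on sessions 1 and 14 being test-only, and on no symptom question sitting in forms or consent material outside the available text. Severity is minor, because the plan describes minimal risk and no planned outcome is affected.

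**What to change.** **Ask.** At the start of sessions 3 to 14, before any device use or post-testing, put one scripted question to the parent, and a simple form of it to the child where able. It asks about any discomfort, unusual tiredness, upset, overload or other symptom during or since the last session. Use identical wording in both arms. Log answers by arm, separately from observed signs, and report them descriptively as children with a symptom out of children asked.

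**Act.** Amend the sentence in the monitoring section on events that preclude continuing. After an SAE (for example a seizure or injury), or a reported symptom judged to be an AE, the investigator responsible for safety reviews the case before that child uses the device again. Mild tiredness or frustration is logged only. A wider hold, triggered by any symptom, would risk losing treatment sessions for little gain.

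**Cost.** There are 12 questions per child (sessions 3 to 14). At an assumed 1 to 2 minutes each, that is 12 × 1 = 12 to 12 × 2 = 24 minutes per child. For six children it is 72 to 144 minutes (1.2 to 2.4 h), and for ten it is 120 to 240 minutes (2 to 4 h). A 30-minute session becomes 31 to 32 minutes, inside the 5-minute tolerance. One log form and one amendment are needed. More mild events will be recorded, and some may need the 48-hour report. The safety role is weekly while sessions are twice weekly, so a review may need an extra contact or delay a session. Parents know which device was used, which may colour their answers.

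**If sessions are complete.** The Outcome Measures table is in the past tense, so this is possible. Check the session forms. If symptoms were not asked about, say so and make no tolerability claim.
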